5.2 Definition of Dose-Limiting Toxicity

- 5.2.1 Grade \geq 3 non-hematologic toxicity will be considered dose limiting, with the following exceptions:
 - 5.2.1.1 Grade 3 fatigue lasting \leq 7 days.

5.2.1.2 Grade 3 diarrhea will only be considered dose limiting if, after 48 hours, it is refractory to treatment as outlined in Section 5.3.2. Grade 4 diarrhea will be dose limiting.

5.2.1.3 Grade 3 nausea and vomiting will be considered dose limiting after 48 hours if it is refractory to maximal anti-emetic therapy and unable to be corrected to Grade 1 or baseline. Grade 2 nausea or vomiting after 72 hours despite three anti-emetogenic agents will also be considered dose limiting.

5.2.1.4 Grade 3 rise in creatinine, not corrected to Grade 1 or baseline after intravenous fluids within 24 hours, will be considered dose limiting. All Grade 4 rises in creatinine will be dose limiting.

5.2.1.5 Grade 3 electrolyte toxicities unable to be corrected to Grade 2 or baseline within 24 hours will be considered dose limiting.

5.2.2 Grade 4 hematological toxicity will be considered dose limiting if it meets the criteria below. Lymphopenia (any grade) will not be considered dose limiting for all

subjects.

- 5.2.2.1 Neutropenia: Grade 4 neutropenia for >5 days without fever or infection will be considered dose limiting. Grade 4 neutropenia of any duration accompanied by fever or infection will be considered dose limiting. Twice weekly blood draws will be needed (after onset of grade 4 neutropenia) to monitor duration of neutropenia for the first 2 cycles. On subsequent cycles (cycle 3 and beyond), weekly blood draws will be monitored at the onset of grade 4 neutropenia.
- 5.2.2.2 Thrombocytopenia: Grade 4 thrombocytopenia will be considered dose limiting. Grade 3 thrombocytopenia associated with bleeding will be considered dose limiting.
- 5.2.2.3 Anemia: Grade 4 anemia will be considered dose limiting.
- 5.2.3 Any neurotoxicity Grade ≥ 2 that is not reversible to a Grade ≤ 1 within 2 weeks will be considered dose limiting.
- 5.2.4 Any non-hematologic Grade 2 toxicity that does not resolve to Grade ≤1 or baseline within 14 days despite adequate treatment as described in Section 5.3 will be considered dose limiting, except for alopecia.

Management and dose modifications associated with the above adverse events are outlined in Section 6.

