5.3.2 Diarrhea

Patients will not be given anti-diarrheal prophylactically. If a patient develops diarrhea, if clinically indicated a test for C. difficile will be ordered. If a patient is found to have C. difficile colitis, appropriate antibiotics will be instituted. If noninfectious diarrhea

develops and does not have an identifiable cause other than study drug administration, anti-diarrheal (such as diphenoxylate HCl 2.5 mg + atropine sulfate 0.025 mg/tablet) dosed according to package insert or loperamide 4 mg PO after the first unformed stool with 2 mg PO every 2 hours as long as unformed stools continue (4 mg every 4 hours while asleep). No more than 16 mg of loperamide should be taken in during a 24-hour period. This regimen can be repeated for each diarrheal episode. Diarrhea will be considered refractory if it does not resolve within 48 hours to Grade 2 with the above suggested regimens.

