6.1 Drug-related toxicity

- 6.1.1 If a patient has a DLT during cycle 1, no further treatment will be administered for that cycle and the dose will be reduced by one dose level for the next cycle.
- 6.1.2 If the patient has a DLT during any subsequent cycle, no further treatment will be administered for that cycle and the dose will be reduced by one dose level for the next cycles and the patient will not be eligible for intra-patient dose escalation.
- 6.1.3 If Grade 3 diarrhea occurs (increase of >6 stools/day over baseline) but resolved to ≤ grade 2 with anti-diarrheal within 72 hours, the patient will receive the same dose on subsequent cycles with anti-diarrheal treatment as stated in Section 5.3.2. If Grade ≥3 diarrhea continues > 72 hours despite treatment, this constitutes a DLT (see Section 5.2) and LMP744 will be dose reduced by one dose level for subsequent cycles.

| Diarrhea grade after 72 hours of anti-diarrheal med | Management/Next Dose for LMP744 | |
|---|--|--|
| \leq Grade 1 | No change in dose | |
| Grade 2 | Resume at same dose level. | |
| Grade 3 | Hold [*] until \leq Grade 2. Resume at one dose level lower, if refractory. ^{**} | |
| Grade 4 | | |
| *Patients requiring a delay of >2 weeks will be taken off protocol therapy. | | |
| **Patients requiring > two dose reductions will be taken off protocol therapy. | | |
| Recommended management: Loperamide antidiarrheal therapy | | |
| Dosage schedule: 4 mg at first onset, followed by 2 mg with each loose motion until diarrhea-free for | | |
| 12 hours (maximum dosage: 16 mg/24 hours) | | |
| Adjunct anti-diarrheal therapy is permitted and should be recorded when used. | | |

6.1.4 If Grade ≥2 nausea and vomiting require anti-emetics, the patient will receive antiemetics prior to the administration of subsequent doses of LMP744 as described in Section 5.3.1.

| Nausea grade after 72 hours of antiemetic support | Management/Next Dose for LMP744 | |
|--|---|--|
| \leq Grade 1 | No change in dose | |
| Grade 2 | Resume at same dose level. | |
| Grade 3 | Hold [*] until \leq Grade 2. Resume at one dose level lower if refractory. ^{**} | |
| Grade 4 | Off protocol therapy | |
| * Patients requiring a delay of >2 weeks will be taken off protocol therapy. | | |
| **Patients requiring > two dose reductions will be taken off protocol therapy. | | |
| Recommended management: antiemetics. | | |

| Vomiting grade after 72 hours of antiemetic support | Management/Next Dose for LMP744 | |

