6.2 Intra-patient Dose Escalation and De-escalation

Intra-patient dose ESCALATION is permitted ONLY if:

- 1. Patients did not experience toxicity >Grade 1 that is possibly, probably, or definitely related to the study drug after one cycle at the initial dose level (subsequent cycles may be delayed up to 14 days past the end of the previous cycle of 28 days to allow for toxicities to resolve).
- 2. Higher doses have been evaluated and completed without a DLT.
- 3. The patient's disease has not progressed.
- 4. There is no concern of cumulative toxicity.

Doses may be escalated by one dose level for every subsequent cycle, provided conditions 1-4 are met, up to the last evaluated dose level NOT associated with DLT.

If a patient experiences DLT during a cycle, the dose will be REDUCED by one level (if there is a lower dose level, see Section 5.1.2) for the next cycle, provided toxicity has recovered to \leq Grade 1 within 14 days after completing a 28-day cycle, and the patient's disease is stable or responding. If a patient is dose reduced twice and still experiences a DLT, then the patient would be removed from the study. If no lower dose level exists, then the patient will be removed from the study.

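### Section 6 gives two different next-cycle doses for Grade 3 diarrhea that settles between 48 and 72 hours of treatment

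*Combined protocol and SAP*

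**What the plan says.** **What makes the event a DLT.** Section 5.2.1.2: "Grade 3 diarrhea will only be considered dose limiting if, after 48 hours, it is refractory to treatment as outlined in Section 5.3.2". Section 5.3.2 supplies the test: "Diarrhea will be considered refractory if it does not resolve within 48 hours to Grade 2" on the suggested regimens. Section 5.2.1.2 also makes Grade 4 diarrhea a DLT, with no time limit.

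**What a DLT does to the dose.** Section 6.1.1, for cycle 1: "no further treatment will be administered for that cycle and the dose will be reduced by one dose level for the next cycle". Section 6.1.2, for later cycles: "the dose will be reduced by one dose level for the next cycles and the patient will not be eligible for intra-patient dose escalation". Section 6.2, for any cycle: "If a patient experiences DLT during a cycle, the dose will be REDUCED by one level". Section 6.3 allows two reductions before removal.

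**What the diarrhea paragraph does to the dose.** Section 6.1.3 covers Grade 3 diarrhea that has come down to Grade 2 or lower "with anti-diarrheal within 72 hours, the patient will receive the same dose on subsequent cycles with anti-diarrheal treatment as stated in Section 5.3.2". Its next sentence deals with Grade 3 or higher: if "diarrhea continues > 72 hours despite treatment, this constitutes a DLT (see Section 5.2"), the dose drops one level. The table below it is headed "Diarrhea grade after 72 hours of anti-diarrheal med", and its Grade 2 row resumes at the same level.

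Section 5.2 closes by leaving management and dose changes to Section 6 as a whole. It does not rank the paragraphs there.

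**The concern.** The DLT definition runs on a 48-hour clock and the diarrhea dosing paragraph on a 72-hour clock. Between the two, an event can be a DLT that requires a reduction and also an event whose dose must be kept. Both instructions are mandatory.

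What is at stake is how an individual patient is dosed. The trial is multicenter, and up to 15 expansion patients are treated at 190 mg/m²/day under this text. Two sites following the protocol faithfully could retreat the same kind of patient at different doses. One of them would be giving the full dose again after an event that Section 5.2 calls dose limiting. The count toward the two-reduction limit in 6.3 would differ as well.

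**Working it through.** The plan states no figure to reproduce, so the check is to trace the rules. Let T be the hours of anti-diarrheal treatment until Grade 3 diarrhea reaches Grade 2 or lower. I take both clocks to start with treatment: 5.3.2 judges response to its regimens, and the 6.1.3 table header counts hours of medication.

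| T | DLT under 5.2.1.2 and 5.3.2? | Dose under 6.1.1 / 6.1.2 / 6.2 | Dose under 6.1.3 and its table | Agree? |
|---|---|---|---|---|
| 48 h or less | No | No reduction triggered | Same | Yes |
| Over 48 h, up to 72 h | Yes | One level lower | Same | **No** |
| Over 72 h | Yes | One level lower | One level lower | Yes |

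Example: Grade 3 at 48 hours, Grade 2 at 60 hours. The event failed the 5.3.2 test, so it is a DLT and the dose is reduced. It also reached Grade 2 within 72 hours, so 6.1.3 keeps the dose. At 72 hours the patient sits in the table's Grade 2 row and never reaches the Grade 3 row with its condition about refractory cases.

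**Size, if such a case occurs.** Dose levels are from 5.1.1, the MTD (level 6) from 5.1.2.2 and the reduction limit from 6.3.
- Window: 72 − 48 = 24 h.
- Next-cycle dose from level 6: 190 or 96 mg/m²/day. Difference 190 − 96 = 94, and 94/190 = 49%.
- Five-day total: 5 × 190 = 950 against 5 × 96 = 480 mg/m², a difference of 470.
- Reductions left: 2 − 1 = 1 (next step 48 mg/m²/day) against 2 − 0 = 2.

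The 49% is the spacing between levels 5 and 6. It says nothing about how often the case arises.

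**Narrower parallel in 6.1.4 (dosing only).** Section 5.2.1.3 makes two kinds of event DLTs: Grade 2 nausea or vomiting persisting after 72 hours despite three agents, and Grade 3 that is refractory at 48 hours to maximal therapy and cannot be brought to Grade 1 or baseline. The 6.1.4 tables read the grade at 72 hours. The first kind lands in the Grade 2 row (same dose). The second, if it has improved by 72 hours, lands in the Grade 2 row or the Grade 1-or-lower row (no change). The generic DLT rules would reduce the dose in each case.

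**The case against.** The best defence is that Section 6 contains event-specific rules that displace the generic DLT rule. There is evidence for this. Grade 4 nausea or vomiting is a DLT, yet the 6.1.4 tables take the patient off therapy where 6.1.1 would reduce one level. Grade 4 neutropenia of five days or less without fever or infection is not a DLT under 5.2.2.1, yet its table reduces the dose. The event tables therefore do not simply follow DLT status, and one could read the plan as counting a DLT at 48 hours but keeping the dose if treatment has worked by 72.

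That observation about the tables stands, but it does not settle the diarrhea case. Section 6.1.3 itself ties the reduction to DLT status under 5.2, nothing presents it as an exception to 6.1.1, 6.1.2 or 6.2, and no text gives it precedence.

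Three other points on that side also stand:
- A reader might infer that 6.1.3 misstates Section 5.2. It does not. Diarrhea still at Grade 3 or higher beyond 72 hours has already failed the 48-hour test, so the sentence is true as a sufficient condition. It is incomplete as a statement of the threshold.
- The nausea and vomiting overlap is narrow. Most Grade 2 cases will not have failed three agents and are not DLTs.
- The team reviews each patient weekly during active treatment (12.2) and may catch a case. The text would still give them two answers.

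**Conclusion.** Wrong as written, and worth correcting. For Grade 3 diarrhea still above Grade 2 after 48 hours of treatment but at Grade 2 or lower by 72 hours, the protocol orders both a one-level reduction and the same dose. If such a case occurs at the expansion dose, the next cycle is 96 or 190 mg/m²/day, and one or two reductions remain, depending on which paragraph the site follows. This rests on both clocks starting with anti-diarrheal treatment.

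The effect is conditional. No affected patient is shown, and the documents give no frequency. Diarrhea is not on the human adverse event list in 7.1.1. Nausea and vomiting are, but without frequencies.

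A reader might go further and infer that DLTs have been miscounted or that the MTD is in doubt. The documents do not support either. Section 5.1.2 points to 5.2 for DLT classification, and 6.1.3 does not say that a 48-to-72-hour case is not a DLT. A site working from 6.1.3 alone could miscode one, which would reach the DLT summary and the dose–DLT regression in 13.1, but that is only a possibility. The MTD is already declared, and nothing here shows that it would change.

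**What to change.** 1. In 6.1.3, change 72 hours to 48 hours in the first sentence and in the table header.
2. Replace the DLT criterion in the second sentence with: 'If the diarrhea is a DLT under 5.2.1.2, follow 6.1.1/6.1.2.' Changing only the number would not be enough, because that sentence also covers Grade 4 diarrhea, which is a DLT at once.
3. Add one note to both 6.1.4 tables, applying to the Grade 1-or-lower and Grade 2 rows: 'unless the event met the DLT definition in 5.2, in which case follow 6.1.1/6.1.2'. Leave the Grade 4 rows as they are.
4. Check existing cycle 1 Grade 3 diarrhea records for any case in the 48-to-72-hour window, and report any whose DLT coding changes.

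With items 1 and 2, the middle row of the table above gives a reduction by every route and the other two rows are unchanged. Stating that 6.1.3 overrides the generic rules would also remove the conflict, but it would sanction full-dose retreatment after a DLT. Moving 5.2 to 72 hours would change the DLT definition after the MTD was declared.

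The cost is a few words in an amendment and one record look-up. There are no added patients or procedures, and the recovery rules in 6.1.5 and 6.2 are untouched.

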|--|---------------------------------|--|
| \leq Grade 1 | No change in dose | |

| Vomiting grade after 72 hours of antiemetic support | Management/Next Dose for LMP744 | |
|--|--|--|
| Grade 2 | Resume at same dose level. | |
| Grade 3 | Hold [*] until \leq Grade 2. Resume at one dose level lower, if refractory. ^{**} | |
| Grade 4 | Off protocol therapy | |
| *Patients requiring a delay of >2 weeks should go off protocol therapy. | | |
| **Patients requiring > two dose reductions should go off protocol therapy. | | |
| Recommended management: antiemetics. | | |

6.1.5 Patients will be allowed to continue treatment for decreased leucocytes, ANC and hemoglobin that recover to a Grade ≤ 2 toxicity and platelets to Grade ≤ 1 . Dose reduction to one dose level lower may also be considered if ≥ 4 occurrences of symptomatic anemia requiring blood transfusion, at the discretion of the clinician.

| Neutropenia | Management/Next Cycle | |
|--|---|--|
| ≤ Grade 1 | No change in dose | |
| Grade 2 | Resume at same dose level. | |
| Grade 3 | Hold [*] until < Grade 2. Resume at same dose level. | |
| Grade 4 | Hold [*] until < Grade 2. Resume at one dose level lower ^{**} | |
| *Patients requiring a delay of >2 weeks will be taken off protocol therapy. | | |
| **Patients requiring > two dose reductions will be taken off protocol therapy. | | |
| Use of growth factors per ASCO guidelines. | | |

| Thrombocytopenia | Management/Next Cycle | |
|--|--|--|
| ≤ Grade 1 | No change in dose | |
| Grade 2 | Hold until \leq Grade 1. Resume at same dose level. | |
| Grade 3 | Hold [*] until < Grade 1. Resume at one dose level lower, if indicated. ^{**} | |
| Grade 4 | Hold [*] until < Grade 1. Resume at one dose level lower. ^{**} | |
| *Patients requiring a delay of >2 weeks will be taken off protocol therapy. | | |
| **Patients requiring > two dose reductions will be taken off protocol therapy. | | |

| Anemia | Management/Next Cycle | |
|--|--|--|
| ≤ Grade 1 | No change in dose | |
| Grade 2 | Resume at same dose level. | |
| Grade 3 | Hold* until < Grade 2. Resume at one dose level lower, if indicated. ** | |
| Grade 4 | Hold [*] until < Grade 2. Resume at one dose level lower. ^{**} | |
| *Patients requiring a delay of >2 weeks should go off protocol therapy. | | |
| **Patients requiring > two dose reductions should go off protocol therapy. | | |

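### Grade 2 nausea or vomiting that is a DLT under 5.2.1.3 is sent back to the same dose by the 6.1.4 tables, while 6.1.1, 6.1.2 and 6.2 require a reduction

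*Combined protocol and SAP*

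**What the plan says.** Section 5.2.1.3 includes one Grade 2 event for these symptoms among the DLTs: "Grade 2 nausea or vomiting after 72 hours despite three anti-emetogenic agents will also be considered dose limiting". Section 5.2 closes by referring the reader to Section 6 for management and dose changes.

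Section 6 then gives two sets of instructions.

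- **General DLT rule.** For cycle 1, Section 6.1.1 says "no further treatment will be administered for that cycle and the dose will be reduced by one dose level for the next cycle". Section 6.1.2 covers later cycles: "If the patient has a DLT during any subsequent cycle, no further treatment will be administered for that cycle", again with a one-level reduction and with loss of eligibility for intra-patient escalation. Section 6.2 repeats the one-level reduction, provided toxicity has come down to Grade 1 or less within 14 days of the end of the 28-day cycle and disease is stable or responding.
- **Symptom tables in 6.1.4.** The headers are "Nausea grade after 72 hours of antiemetic support | Management/Next Dose for LMP744" and "Vomiting grade after 72 hours of antiemetic support | Management/Next Dose for LMP744". In both tables the middle row reads "Grade 2 | Resume at same dose level". Neither the lead-in to 6.1.4 nor the footnotes (delay over two weeks, more than two reductions, recommended antiemetics) mentions DLT status.

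The Grade 3 rows do carry a qualifier. The vomiting table says "Resume at one dose level lower, if refractory", and the nausea table says the same in substance. For diarrhea, Section 6.1.3 states outright that persistent Grade 3 or worse is a DLT and leads to a reduction.

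**The concern.** The 6.1.4 tables are read at 72 hours of antiemetic support, and 5.2.1.3 also sets its Grade 2 DLT at 72 hours. A patient who is still Grade 2 then, despite three agents, has a protocol-defined DLT and also falls in the Grade 2 row. One rule stops the cycle and lowers the dose; the other resumes at the full level. The protocol gives no order of precedence.

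What is at stake is the dosing of individual patients. A site that follows the row gives the full dose to someone for whom 6.1.1 or 6.1.2 requires a reduction. Where the patient does not meet the 6.2 conditions, none of 6.1.1, 6.1.2 or 6.2 supports same-level dosing either. Nausea and vomiting are both on the list of possibly related events in Section 7.1.1. The trial is multicenter, so sites could resolve the conflict differently. The rows also apply in the expansion cohort, planned at 15 patients on 190 mg/m²/day (Section 5.1.2.2).

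**Working it through.** The plan states no figure on this point, so there is nothing to reproduce. The check compares the rules for one patient and then sizes the dose difference.

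**Step 1: the same patient under each rule.** Take Grade 2 nausea or vomiting at 72 hours, on three antiemetics.

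- Under 5.2.1.3 the event is a DLT.
- Under 6.1.1 or 6.1.2 there are no more infusions that cycle, and the next cycle is one level lower.
- Under 6.2 there is a one-level reduction, only after recovery to Grade 1 or less and with stable or responding disease.
- Under the 6.1.4 Grade 2 row the patient resumes at the same level, and may do so while Grade 2 is still present.

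**Step 2: does the meaning of the row remove the conflict?** The 6.1.4 headers speak of the next dose, whereas the hematology tables in 6.1.5 are headed by cycle (for example "Neutropenia | Management/Next Cycle"). The row could therefore mean a later infusion in the same cycle or the next cycle. On the first reading, 6.1.1 and 6.1.2 allow no infusion. On the second, they require one level lower. The conflict remains either way.

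**Step 3: size on the next-cycle reading.** Inputs: Level 6 = 190 and Level 5 = 96 mg/m²/day (Section 5.1.1); MTD = Level 6 (Section 5.1.2.2).

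- Difference: 190 − 96 = 94 mg/m²/day.
- Ratio: 190 / 96 = 1.98.

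**Step 4: size on the same-cycle reading, cycle 1.** Two assumptions are needed because the protocol does not settle them: infusions start 24 hours apart, and the 72 hours run from the first antiemetic. Section 5.3.1 allows no prophylactic antiemetic before the first dose, so the first antiemetic is at time h > 0.

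- Infusion starts: 0, 24, 48, 72 and 96 h.
- 72-hour mark: 72 + h, which is after the Day 4 start.
- If 0 < h < 24, then 72 + h < 96 and only Day 5 remains: 190 versus 0 mg/m² for one infusion.
- If h ≥ 24, then 72 + h ≥ 96 and no later infusion remains.

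The range is 0 to 1 infusion. It applies to cycle 1 only, since in later cycles 5.3.1 permits antiemetics before the first infusion.

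**Step 5: what is not affected.** DLT status follows 5.2, and escalation follows the DLT count in cycle 1. The 6.1.4 rows enter neither, so the 3+3 decisions and the MTD stand.

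**The case against.** The best case for the current text is that the DLT instruction is already complete. Sections 6.1.1 and 6.1.2 open Section 6.1, cover every DLT and exempt no symptom, and 6.2 repeats the reduction. On this view the tables manage toxicity by grade, the general rules manage DLTs, and no one would use a table to undo a DLT rule. That is a plausible reading, but no sentence states it. A reader could equally take the symptom-specific table as the controlling detail. The protocol makes the DLT link explicit for diarrhea and qualifies the Grade 3 rows, so its absence from the Grade 2 rows is noticeable.

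Several narrower points stand as limits:

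- The tables do not count agents, and 5.3.1 names only a first and a second, so the Grade 2 row mostly describes ordinary events for which the same dose is right. The overlap is the three-agent subset, plus events that later meet 5.2.4.
- If the 72-hour clock starts at the third agent, and that agent is added on Day 2 or later, no cycle 1 infusion is affected. The range above already includes zero.
- The resume-at-Grade-2 mismatch with 6.2 is part of the same conflict and should not be counted twice. The Grade 3 rows, which hold only to Grade 2, share that mismatch.
- Fifteen is the planned expansion size; under Section 13.1 accrual stops at 6 usable biopsy pairs, so fewer patients may be exposed.
- The weekly review of each patient in Section 12.2 may catch single cases, but it does not tell the team which text applies.

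It is also true that 5.2.4 (Grade 2 unresolved at 14 days) cannot be known at 72 hours. Mentioning it in the row does no harm, because it applies only if the criterion has been met by the time of the next dose.

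**Conclusion.** The concern holds. For Grade 2 nausea or vomiting that meets a DLT criterion, the protocol gives opposite dosing instructions and no order of precedence. Followed literally at the expansion dose, the Grade 2 row gives 190 rather than 96 mg/m²/day in the next cycle, assuming the 6.2 conditions are met. On the same-cycle reading it permits at most one cycle 1 infusion where none is allowed, under the clock and spacing assumptions above. These figures are dose spacings, not expected harm: the documents give no count of such events, and the affected group is narrow. Because the conflict concerns re-dosing after a DLT and is simple to remove, it should be corrected.

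**What to change.** Qualify the Grade 2 row in both 6.1.4 tables. Suggested wording: *Same dose level, unless the event met a DLT criterion in 5.2 (5.2.1.3 or 5.2.4). If it did, give nothing further that cycle and restart one dose level lower under 6.1.1 or 6.1.2, subject to the recovery and disease-status conditions in 6.2.*

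This keeps same-dose resumption for ordinary Grade 2 events. It costs two table rows in an amendment and changes no DLT definition, procedure, visit or patient number.
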